5.7 Withdrawal of Subjects

- **Describe any anticipated circumstances under which subjects will be withdrawn from the research without their consent.**

There are no anticipated circumstances under which subjects will be withdrawn without their consent.

- **Describe the consequences of a subject's decision to withdraw from the research and the procedures for orderly termination of participation by the subject (e.g., the subject contacting the investigator for an end-of-study visit).**

This is an RCT but as will be clear in the information letter, patients may choose to withdraw from the study at any time. If IVR calls are not answered, study staff will attempt to contact patients (up to 5 or 6 attempts will be made, including leaving voice mails and providing call-back information for participants who are not home) to determine whether they wish to continue participating. Participants who indicate they have changed their mind and no longer wish to continue in the study will not be contacted again.

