5.5 Study Evaluations

- **Describe all evaluations to be conducted (including screening; tests/questionnaires that will be administered; any procedures that subjects will be required to complete) and data collection methods. Include materials as an appendix or separate attachment.**

Potential participants will be sent an introductory packet from the AAVA. After one week, the coordinator will telephone those Veterans who did not opt-out, and if the patient is interested, the coordinator will administer the Brief Screener by phone and determine whether that Veteran meets the criteria of having a clinically meaningful symptom burden score (1 or higher on any one symptom, as a measure of low function or high symptom burden) on at least one item. Once the Veteran has been deemed eligible and the baseline survey has been administered, the veteran will be randomized to the automated telephone system or enhanced usual care (information about self-management).

Veterans randomized to the automated telephone system intervention will receive 4 automated phone calls over a 3-month period: 1 at study start and then once a month for 3 months. These calls will last approximately 15 minutes and will include questions about symptoms, will allow the veteran to identify a goal to work on, and help the veteran take steps towards reaching their goal and managing their symptoms. At the end of each call, the veteran will also have the option of listening to an audio testimonial tailored on priority symptom area. Following each call, the veteran will receive a personalized newsletter that will provide more details regarding their symptoms and strategies to help them manage their symptoms. Each newsletter will be 4 – 8 pages in length. The automated system will try to reach the veteran up to eight times over the course of 4 days (see IVR call schedule). If the veteran has not completed the call by day 3 of the call window, study staff will make up to 5 or 6 attempts to contact the patient (including leaving messages) to verify the phone number and preferred call time. If the veteran has still not completed the call by day 5 of the call window, study staff will again make up to 5 or 6 attempts to contact the patient. Following each reminder call, study staff have the option to initiate additional IVR calls should veteran be agreeable.

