Veterans randomized to this group may also be contacted to participate in a 30 to 40-minute audio-recorded phone interview to find out about their experience with the program. These interviews will be conducted by the research staff at the Ann Arbor VA in Ann Arbor, MI. During the 12-month survey, veterans will be asked if they are interested in participating in the interview.

Veterans randomized to the control group will receive one 4-page newsletter with educational information about symptoms and symptom management, and will complete a survey over the phone at enrollment and at 5 and 12 months after starting the study.

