Telephone surveys of both intervention and control groups to obtain baseline and follow-up measures will be conducted at three time points: baseline, five months, and 12 months post-enrollment. Hard copies of follow-up surveys will be sent to any participants expressing preference for completing the survey by paper and participants we are unable to reach by phone. Survey content will be finalized by our study team using established approaches during year 1 and pilot tested among prostate cancer survivors affiliated with the VAAHS prior to use in the trial. Each survey will be administered by the VA coordinator over the telephone. After each of these three assessments, both intervention and control group patients will be called by the IVR system for standardized administration of the EPIC. Baseline surveys will be done prior to randomization. Beginning approximately 4 months following enrollment, initial attempts will be made by the coordinating team to contact the participant by phone to complete the Time 2 survey, and approximately 11 months following enrollment to complete the Time 3 survey. For all 3 surveys, up to 5 or 6 attempts will be made to complete the survey, including leaving voice mails and providing call-back information for participants who are not home. Times to complete the surveys will be scheduled as desired by participants. Finally, if participants are unable or unwilling to complete the survey by telephone, a paper-and-pencil survey will be mailed to them with a return envelope. Participants who fail to return the paper survey within one month may be sent a second paper survey by mail. In addition, a reminder newsletter will be sent to participants 1-2 months prior to their expected 12-month follow-up. All participants completing the 12-month assessment will be sent an "early results" newsletter showing some preliminary survey results and thanking participants for their contribution to the study.

Patients are free to skip any survey questions administered by study staff that they would prefer not to answer. However, because the newsletters are tailored based on responses to questions administered by the automated telephone system, these questions are not optional. Nevertheless, patients are free to hang up the phone if they prefer not to complete an IVR call. Patients will also have the option to call into the IVR system using a toll free number if they prefer not to wait to complete their call.

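### Unanswered automated calls lead to a question about leaving the study, a no ends all contact, and the intervention arm meets that trigger more often before the 5-month assessment

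*Combined protocol and SAP*

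**What the plan says.** Section 5.7 gives one procedure for withdrawal. It starts from missed automated calls: "If IVR calls are not answered, study staff will attempt to contact patients", with up to 5 or 6 attempts, "to determine whether they wish to continue participating". It then states the consequence: "Participants who indicate they have changed their mind and no longer wish to continue in the study will not be contacted again". The section does not limit the trigger to one arm or to one kind of IVR call.

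Section 5.5 sets the calls. In the intervention arm, "Veterans randomized to the automated telephone system intervention will receive 4 automated phone calls over a 3-month period". In the control arm, "Veterans randomized to the control group will receive one 4-page newsletter with educational information about symptoms and symptom management", with no programme calls. Both arms also get outcome calls: "After each of these three assessments, both intervention and control group patients will be called by the IVR system for standardized administration of the EPIC".

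Section 5.5 also describes what staff do when a programme call is not completed by day 3 of its window, and gives a different purpose: "to verify the phone number and preferred call time". A second round follows: "If the veteran has still not completed the call by day 5 of the call window, study staff will again make up to" (the sentence goes on to give the same number of tries as the first round). That section says nothing about asking whether the man wants to remain in the study. It also lets a man hang up on an IVR call that he does not want to finish.

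**The concern.** Stopping a behavioural programme and leaving outcome follow-up are different decisions. Section 5.7 offers only the second, and raises it when a man has not been answering. A man who is tired of the automated calls but would have answered two more surveys has no described way to say so. If he answers no, the study loses his EPIC, confidence and self-management outcomes, and the mailed paper survey that section 5.5 keeps for hard-to-reach men is closed to him as well.

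Most of the calls that can set this off belong to the intervention arm and fall before the 5-month assessment, which section 5.6 names as the primary time for Aim 1. Missing outcomes could then depend both on arm and on engagement with the intervention. Section 5.6 does not guard against this. Its attrition allowance is the same in both arms, it mentions missing data only as something to examine during data verification, it states no method for missing outcomes, and its mixed model uses men seen at both follow-ups.

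**Working it through.** **1. Count of calls that can trigger the contact** (sections 5.5 and 5.7)

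- Intervention arm: 4 programme + 3 EPIC = 7.
- Control arm: 3 EPIC = 3.
- Before the 5-month survey: 4 programme + 1 EPIC (after baseline) = 5, against 1.

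The count uses the section 5.5 schedule. Section 5.2 describes the automated calls to participants as weekly. The two need reconciling, and the count would change with the answer.

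**2. The plan's own sample size** (section 5.6)

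Inputs: difference 0.33 SD, power 90%, α 0.0125, baseline correlation 0.5. Sidedness is not stated; two-sided reproduces the figure.

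n per arm = 2 × (z for 1 − α/2 + z for power)² × (1 − r²) / δ² = 2 × (2.498 + 1.282)² × 0.75 / 0.33² = 197, so 394 in total. This matches.

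Completers: 550 × 0.85 × 0.85 = 397. This also matches.

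**3. Effect of extra loss in one arm**

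The documents give no rate of exit by this route and no outcome gap, so both are assumed. There are 550 / 2 = 275 men per arm. Planned retention is 0.85 at 5 months and 0.85² = 0.7225 at 12 months.

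Let x be the extra loss in the intervention arm, in percentage points of those randomised. Let g be how much smaller the improvement of those extra men would have been than that of the men retained, in SD of the outcome. The gap must be in change, because the primary outcome is change from baseline. The completers' mean then overstates the intervention mean by

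bias = (x / planned retention) × g.

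At 5 months (in SD):

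| Extra loss | g = 0.25 | g = 0.5 | g = 1.0 |
|---|---|---|---|
| 5 points | 0.015 | 0.029 | 0.059 |
| 10 points | 0.029 | 0.059 | 0.118 |
| 20 points | 0.059 | 0.118 | 0.235 |

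At 10 points (275 × 0.10, about 28 men), this is 9%, 18% or 36% of 0.33 SD. At 12 months the same 10 points give 0.035, 0.069 and 0.138 SD. A negative g (men leaving because they had improved) gives the same sizes with the opposite sign.

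**4. Power**

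With 10 points of extra loss in the intervention arm only, power for 0.33 SD falls from 94.8% to 93.2% at 5 months and from 90.3% to 87.6% at 12 months. With 20 points it falls to 90.9% and 83.7%. The loss of power is modest, and the larger risk is bias.

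**The case against.** A reader might go further than the text in four ways.

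- *Controls never face this question.* They can. They are due three IVR calls for the EPIC, and section 5.7 speaks of unanswered IVR calls in general. Exposure is unequal, not absent in controls.
- *A man who stops the programme always loses his outcomes.* He does not. Contact ends only when he says that he no longer wants to be in the study. Section 5.5 lets men hang up, and its survey follow-up does not depend on having completed the programme calls.
- *Each programme call window carries an invitation to leave.* The documents do not say so. Section 5.5 describes the contact within a window as a check on phone number and call time. What is supported is that the two sections give different purposes and must be reconciled. The contact script is not available, so how staff put the question is unknown.
- *The bias favours the intervention.* That needs men lost this way to have improved less. It is plausible for poorly engaged men, but men who feel better may also stop.

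It is also fair to say that the loss rates are assumed, that 20 points from this route alone would exceed the plan's whole 15% allowance per assessment, and that the lowest case is negligible. Asking whether a man wishes to continue is also a reasonable check that participation is voluntary.

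These points limit the claim but do not remove it. Hanging up skips one call; it is not a way to leave the programme and stay in follow-up, and a later unanswered call can still lead to the section 5.7 contact. The different purpose in section 5.5 does not cancel the section 5.7 rule.

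**Conclusion.** The concern holds in a limited form. Section 5.7 ties a question about leaving the study to unanswered automated calls, makes a no final, and describes no way to give up the programme but keep the outcome assessments. Nothing elsewhere in the documents supplies that option. The size and direction of any bias rest on the assumptions shown above and cannot be settled from the documents. Only outcomes that need contact are exposed. Aim 2 draws mainly on VA records, although the plan does not say whether extraction continues after withdrawal. The change is worth making because it is cheap, and outcomes not collected at 5 and 12 months cannot be recovered later.

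**What to change.** In section 5.7 and the contact script, for both arms, separate two choices:

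- (a) stopping the programme calls and newsletters (where the arm has them), or the automated calls, while still being contacted for the 5- and 12-month assessments;
- (b) stopping all study contact.

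Apply the no-further-contact rule only to (b). Record the choice and its date, by arm. Analyse men who choose (a) in their randomised arm with the outcomes collected. Since section 5.5 describes the EPIC as given by IVR, state how it will be obtained from a man who declines automated calls. Reconcile the purpose of the missed-call contact between sections 5.5 and 5.7.

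Staff need not be barred from asking about leaving; once the choices are separate, the question no longer costs an outcome that the man was willing to give. The change reduces loss at source but does not replace a stated method for outcomes that are still missing.

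The cost is an IRB wording amendment and a slightly longer script. The follow-up contacts are already planned.

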6.0 Reporting

- **Include procedures for reporting unanticipated problems, serious adverse events, and protocol deviations.**

Reports of related SAEs and UAPs and protocol deviations will be made by the study team member who discovers the event, the site coordinator, or the project manager to the VA Central IRB (CIRB). The Ann Arbor project manager should be notified at the same time a report is made if the report is coming from another site's study team member. Any unanticipated related incidents involving a death at any of the 3 study sites will be reported immediately to the CIRB. Any unanticipated related incidents involving SAEs and UAPs meeting the definition of serious will be reported within 5 business days of discovery to the CIRB secure SharePoint site dedicated to this purpose. AEs and UAPs that are not related are to be reported to Ann Arbor project manager as they are discovered, and will be reported to the CIRB in summary at the time of continuing review/project closure. Protocol deviations/violations that are likely to substantially adversely affect 1) the rights, safety, or welfare of a participant; 2) a participant's willingness to continue participation; or 3) the integrity of the research data, including VA information security requirements will all be reported within 5 working days of being made aware of the occurrence. These will be reported through the secure SharePoint site dedicated to this purpose.

It is possible the automated system and follow-up surveys may uncover certain symptoms that warrant medical attention. The 2 possible symptoms that the automated system could uncover is blood in stools and/or urine, though the likelihood of either of these is low. If a study participant reports blood in stool and/or urine (or other concerning symptoms requiring the input of a physician), study staff will contact the participant to confirm the report. For all participants verifying current or recent symptoms, we will enter a progress note in the patient's medical chart with a description of the patient's reported symptoms and a request for follow-up and add the appropriate provider(s) as additional signers on the note. This plan has been reviewed and approved by all the MDs on the study. In the event a study participant has no assigned provider(s) at the VA appropriate for follow up of reported concerning symptoms, study staff will contact the participant directly and encourage him to notify his primary care (or other) provider of said symptoms. Should the study participant express concerns or request additional information, or in the event the participant has no assigned community-based provider, the patient will be contacted by a study MD. In the event we

are unable to reach participants by phone who have no VA assigned provider, study staff will send a letter by mail encouraging them to notify their provider of the reported symptoms.

Complaints from participants regarding VA medical care unrelated to the study should be documented by study staff and reported to the local Patient Advocate Liaison.

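### The symptom follow-up pathway has no fallback letter or note for a man with a VA provider who reports blood in stool or urine and cannot be reached

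*Combined protocol and SAP*

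**What the plan says.** Section 6.0 (Reporting) accepts that the automated calls and the follow-up surveys may bring to light symptoms needing medical attention. For the automated calls it names two: "The 2 possible symptoms that the automated system could uncover is blood in stools and/or urine". It rates the likelihood of either as low.

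The pathway then has these steps:

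- After a report of blood, or of another concerning symptom that needs a physician's input, "study staff will contact the participant to confirm the report". No number of attempts, time limit or mode of contact is given.
- "For all participants verifying current or recent symptoms, we will enter a progress note in the patient's medical chart". The note asks for follow-up, and the appropriate providers are added as signers.
- A man with no suitable VA provider is encouraged directly to tell his own provider. A study physician contacts him if he has concerns, wants more information or has no community provider.
- If staff "are unable to reach participants by phone who have no VA assigned provider, study staff will send a letter by mail", the letter encourages the man to tell his provider.

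**The concern.** The two written outputs of the pathway carry different conditions. The note depends on verification, which requires that the man was reached. The letter depends on not being reached and also on having no assigned VA provider. A man who has a VA provider and is not reached falls between the two.

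At stake is whether a report that the plan treats as possibly needing medical attention gets beyond the study team. If contact keeps failing, nothing in the text moves the information to his provider or sends him a written prompt. The plan foresees failed phone contact, because it writes a letter rule for it, but it restricts that rule to one subgroup.

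**Working it through.** No arithmetic on rates or power applies. The check lists the branches of the Section 6.0 pathway and then looks elsewhere for a rule that covers the empty one.

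**Branches**

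| VA provider | Outcome of contact | Action specified |
|---|---|---|
| Yes | Reached, symptom verified | Chart note with provider as additional signer |
| No | Reached, symptom verified | Chart note as well (it applies to all who verify), plus encouragement to tell his own provider, and study physician contact in stated circumstances |
| No | Not reached by phone | Letter by mail |
| Yes | Not reached | The general duty to contact continues; no letter or note |

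Men who are reached and do not verify the symptom have been spoken to and are outside the point. Among the two not-reached branches, the count with a specified fallback is 1 of 2. This counts branches of the procedure, not men.

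**Search for a covering rule**

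- Section 5.5, missed automated calls: staff make up to 5 or 6 "attempts to contact the patient (including leaving messages) to verify the phone number and preferred call time". The purpose is to complete the call.
- Section 5.5, surveys: "up to 5 or 6 attempts will be made to complete the survey". The purpose is data collection.
- Section 5.7, unanswered automated calls: staff try to reach the man "to determine whether they wish to continue participating". The purpose is retention.
- Section 5.1, support from an investigator: this is triggered when a participant voices a concern on a call with staff, so it cannot apply to a man who is not reached.
- Sections 6.0 and 8.0, adverse events and unanticipated problems: these govern reporting to the IRB, not notice to the man or his provider.

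None supplies a letter or note for the fourth branch.

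**Can the branch occur?** The man has just reported a symptom, so one might assume he is reachable. Section 5.5 says "Patients will also have the option to call into the IVR system using a toll free number", so a completed automated call does not by itself show that he answers calls from staff. The possibility is logical only; the documents do not show that men who dial in are hard to reach. A report on a paper survey is conceivable for other concerning symptoms, but the documents do not show that the paper survey asks about blood.

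**Is a letter feasible?** Yes. Section 5.2 makes entry of the participant's address a condition of joining the study. Section 5.5 already mails paper surveys to men who cannot be reached by phone, whatever their provider status.

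**How many men?** This cannot be derived. It would need the symptom reporting rate, the share of men with a VA provider and the failure rate of confirmation contacts. The documents give none of these.

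**The case against.** The strongest reply is that the branch is not without an action. The duty to contact applies to every man who reports a symptom, has no cap and is not limited to the telephone, so staff may already write to him. For the report to go no further, all contact would have to fail or stop, and the plan does not tell staff to stop. The man also knows his own symptom. Other scheduled contact narrows the case: intervention-arm men get automated calls at the start and monthly for three months, and both arms are surveyed at baseline, 5 and 12 months. The restriction on the letter may be deliberate, since it closes the sub-pathway for men who have no VA provider to add as a signer, and the study physicians approved the plan. The dial-in option is described as a convenience and is weak evidence of unreachability. Operating instructions, such as the IVR call schedule the protocol mentions, may say more and could not be checked.

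Most of this bears on weight, and it stands to that extent: the case is probably rare and the consequence limited. It does not close the gap. Permission to write is weaker than an instruction to write, and the text gives that instruction for one group of unreached men and omits it for the other. None of the scheduled contacts is assigned to confirming a symptom. If the intent is that a man with a VA provider gets a chart note regardless, the text says otherwise, because the note depends on verification.

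**Conclusion.** The point holds. As written, the pathway gives a fallback to unreached men without a VA provider and none to unreached men with one, who are left with an open-ended duty to contact. This rests on the wording of Section 6.0 and on the absence of a covering rule in the sections available. It assumes that no operating instruction outside these documents fills the gap.

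The size is small. Three things must coincide: a reported symptom, an assigned VA provider and failed confirmation. The plan itself expects blood to be reported seldom. The sample size, endpoints, estimates and error rates are unaffected. The correction is still worth making, because it concerns participant safety and costs almost nothing. Confidence is high for the gap in the text; how often it would matter in practice is unknown.

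**What to change.** In the last sentence of the symptom pathway in Section 6.0, delete the six-word clause that limits the letter to men without an assigned VA provider. The sentence remains grammatical and then covers every man with a reported symptom who cannot be reached by phone. The letter's message, to tell his provider, suits men with a VA provider equally well.

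Two additions are optional and for the study physicians to decide: a chart note marked as unconfirmed with the provider as signer, and a set number of failed attempts after which staff act.

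The cost is a minor IRB amendment. The letter is already in the pathway and the addresses are already held. The downside is a few letters about reports that were never confirmed.
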